### **8.1.5 Secondary Efficacy Endpoints**

The secondary efficacy endpoints are:

- Progression-free survival (PFS) based on the CRAC per RECIST v1.1
- Patient reported outcomes (PROs) – physical functioning domain at C2D1 for Rovalpituzumab tesirine arm and C3D1 for topotecan arm
- Objective response rate (ORR: CR + PR) based on the CRAC per RECIST v1.1
- Clinical benefit rate (CBR: CR + PR + SD) based on the CRAC per RECIST v1.1
- Duration of objective response (DOR) based on the CRAC per RECIST v1.1

PFS is defined as the time from randomization to documented CRAC-assessed disease progression based on RECIST v1.1 or death from any cause (whichever occurs earlier). For the analysis of PFS, data for subjects without disease progression or death will be censored at the time of the last radiographic assessment (or, if no radiographic assessment was performed after the baseline visit, subject's data will be censored at the time of randomization plus 1 day). Data from subjects who are lost to follow-up will be included in the analysis as censored observations on the last date of radiographic assessment that the subject was documented to be progression free. The PFS rates at 6 and 12 months and corresponding 95% CIs will also be estimated using KM estimates on the PFS curve for each arm. Methods for PFS analysis are similar to those described for the OS endpoint.

A sensitivity analysis of PFS will be performed based on investigator-assessed disease progression or death from any cause. Accounting for subjects who initiated a new anti-cancer therapy prior to progressive disease or death, an additional sensitivity analysis of PFS will be performed, considering the date of last radiographic assessment by CRAC prior to or on the start date of new anti-cancer therapy/procedure, as a censoring date.

Analyses of ORR and CBR will be performed for the randomized subjects with at least one measurable disease at baseline. For subjects whose tumors meet the criteria of partial or complete response (PR or CR), tumor measurements must be confirmed by repeat assessments performed no less than 4 and no more than 6 weeks after the criteria for response are first met.

Objective response rate includes confirmed complete response (CR) and confirmed partial response (PR) assessed by the CRAC based on RECIST v1.1 from the date of randomization until disease progression or death, whichever comes first. A subject who did not meet CR or PR, including those who did not have post-baseline radiological assessments will be considered as non-responder.

Comparison of ORR will be carried out using a one-sided Cochran-Mantel-Haenszel (CMH) test, stratified by the randomization stratification factors. Odds ratio will be presented with two-sided 95% CI. The difference in ORR will be provided with two-sided 95% CI. Rates and corresponding 95% exact CI will be calculated by Clopper-Pearson method for each arm. Sensitivity analysis based on investigator-determined ORR will also be performed.

Clinical benefit includes complete response (CR), partial response (PR), and stable disease (SD) assessed by the CRAC based on RECIST v1.1 from the date of randomization until disease progression or death, whichever comes first. A subject who did not meet CR, PR, or SD, including those who did not have post-baseline radiological assessments, will be considered as non-responder. The same statistical methodology will be used as that for ORR endpoint.

A sensitivity analysis of ORR and CBR will be performed, accounting for subjects who initiated a new anti-cancer therapy. Modified endpoints of ORR and CBR, defined as rates of response from the date of randomization until initiation of new anti-cancer therapy/procedure, disease progression, or death, whichever comes first, will be analyzed using the same methodology as that for the endpoints of ORR and CBR.

Only subjects with an objective response will be included in the analysis of duration of response (DOR). DOR is defined as the time between the date of first response (CR or PR by CRAC, whichever is recorded first) to the date of the first documented tumor progression (assessed by CRAC per RECIST 1.1) or death due to any cause, whichever comes first. If a subject is still responding (i.e., has not progressed nor died after CR or PR), then the subject's data will be censored at date of the last radiographic assessment by CRAC. Methods for DOR analysis are similar to those described for the OS endpoint.

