**Disease/Response Assessment (Radiographic Imaging)**

Treatment response will be assessed by radiographic assessment at protocol-specified time points as outlined in the [Appendix C](#) and [Appendix D](#), Study Activities Tables. Diagnostic quality, spiral CT scans are recommended; other CT methods or MRI may be used if performed consistently throughout the study for each individual subject. Scans of the chest and abdomen must be obtained; scans of the neck and pelvis must also be obtained if there is documented or suspected involvement in these regions. Screening radiographic assessment must include brain MRI/CT. Only non-CNS disease will be considered measurable. Disease response will be determined by the investigator at each assessment according to RECIST v1.1 ([Appendix H](#), Response Evaluation Criteria for

Solid Tumors (RECIST) v 1.1). Radiographic assessments must be scheduled so that the results are known prior to the treatment visit.

Effusion (pleural, pericardial, etc.) assessments will be performed at each radiographical assessment and any new findings communicated to the investigator prior to the next dose of investigational product. Effusions should contribute to disease status assessment per RECIST v.1.1 only if confirmed malignant by cytology or otherwise clearly disease-related; if disease progression is suspected solely based on the appearance of new or increase of existing effusions, confirmation of malignant nature of such effusions is strongly recommended prior to making the decision on treatment discontinuation due to known adverse event profile of rovalpituzumab tesirine. If collected, effusion fluid must be tested centrally and/or locally for cytology if disease progression due to appearance/worsening of effusion is suspected.

For subjects whose tumors meet the criteria of partial or complete response (PR or CR), tumor measurements must be confirmed by repeat assessments performed no less than 4 and no more than 6 weeks after the criteria for response are first met.

Isolated CNS-only progression will not require removal of the subject from therapy. Refer to Section 5.2.3.3, Allowed Concomitant Therapy for details associated with CNS only progression.

The EOT radiographic assessment may be omitted if the previous radiographic assessment was performed within the preceding 6 weeks.

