- q. Diagnostic quality, spiral CT scans are recommended; other CT methods or MRI may be used if performed consistently throughout the study for each individual subject. Scans of the chest and abdomen must be obtained; scans of the neck and pelvis must also be obtained if there is documented or suspected involvement in these regions. Screening scans may be performed within 28 days prior to randomization. Disease response will be determined by the Investigator at each assessment according to RECIST v1.1. Effusion (pleural, pericardial, and etc.) assessments will be performed by a radiologist at each radiographical assessment and any new findings communicated to the Investigator prior to the next dose of investigational product. Effusions should contribute to disease status only if confirmed malignant by cytology. Scheduled tumor assessments will not be affected by delays in therapy and/or drug holidays. Subjects will continue to be monitored by the same diagnostic method throughout the study.
- r. May be omitted if assessment was performed within the preceding 6 weeks.
- s. Radiographic assessments will occur every 6 weeks ( $\pm$  1 week) for the first 30 weeks then every 9 weeks ( $\pm$  1 week) until progression or death. If the subject qualifies to receive 2 additional cycles of Rova-T, radiographic assessments will continue to occur every 6 weeks for the first 30 weeks and then every 9 weeks until second progression or death.
- t. MRI/CT of the brain is required at screening. Subsequent MRI/CT of the brain post screening is required only when clinically indicated (e.g., CNS metastasis history and if CNS progression is suspected).
- u. PRO assessments are required at Screening and before infusion on C1D1.
- v. At each cycle, approximately 6 mL of blood will be collected by venipuncture for pharmacokinetic (PK), Anti-therapeutic antibody (ATA), and neutralizing antibodies (nAb) testing. The pre-infusion sample will be collected prior to dosing on Day 1 (–3 business days window is permitted) and the second sample will be collected 30 minutes ( $\pm$  10 minutes) post-infusion. Only one collection will be required at the EOT visit. The date and time of each sample collected will be recorded to the nearest minute.
- w. Tumor material must be collected to confirm DLL3 expression. Subjects that provide consent for DLL3 testing at any time after initial diagnosis must be registered in IRT.

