11.0 Efficacy Analysis

11.1 General Considerations

Unless otherwise specified, all efficacy analyses described below will be performed on the Randomized Set. Efficacy endpoints of response and progression used in analyses will be based on Central Radiographic Assessment Committee (CRAC). Disease progression will be defined as progression of disease according to RECIST v1.1. For subjects whose tumors meet the criteria of partial or complete response (PR or CR), tumor response must be confirmed by repeat measurements performed no less than 4 and no more than 8 weeks after the criteria for response are first met.

For change from baseline analysis of QOL measures, patients with missing baseline value will be excluded. Descriptive summaries for the efficacy endpoints will be reported by treatment groups. These summaries will also be reported at the individual levels of each stratification factors.

The statistical comparisons for the primary and secondary endpoints will be done according to the multiplicity adjustment plan described in Section 5.7.2 to preserve the familywise one-sided type 1 error rate to 0.025. The statistical comparisons for all the other exploratory efficacy endpoints will be performed at a nominal one-sided 2.5% significance level. Confidence intervals for parameters (e.g., median survival times, HR) will be constructed with 2-sided 95% confidence level, whenever applicable. No type I error adjustment for multiple comparisons will be carried out for these exploratory endpoints.

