discontinued the study drug. Data from subjects who are lost to follow-up will be included in the analysis as censored observations on the last date of radiographic assessment that the subject was documented to be progression free.

Analysis methods for PFS endpoint are similar to those described for the OS endpoint. The PFS rates at 6, 9 and 12 months and corresponding 95% CIs will also be estimated using KM estimates on the PFS curve for each arm.

Clinical Benefit Rate (CBR)

Subjects with clinical benefit includes those who achieve confirmed complete or partial response (CR or PR), or stable disease (SD) for at least 12 weeks (2 tumor assessments) as adjudged by the CRAC based on RECIST v1.1.

The clinical benefit rate (CR, PR, and SD) rate will be reported with exact (binomial) two-sided 95% CI for each treatment arm.

CBR will be compared between treatment arms using a Cochran-Mantel-Haenszel (CMH) test, stratified by the randomization stratification factors. The difference in CBR will be summarized with two-sided 95% CI. Rates and corresponding 95% exact CIs will be calculated by Clopper-Pearson method for each arm. Sensitivity analysis based on investigator-determined CBR will also be performed.

Objective Response Rate (ORR)

Analysis of ORR will be performed for the randomized subjects with measureable disease at baseline.

Objective response includes complete response (CR) and partial response (PR) assessed by the CRAC based on RECIST v1.1. Subjects who do not achieve CR or PR, including those who do not have post-baseline radiological assessments will be considered as non-responders.

The same statistical methodology will be used as that for CBR endpoint.

Duration of Response (DOR)

Only subjects with a confirmed objective response will be included in the analysis of duration of response (DOR).

DOR is defined as the time between the date of first response (CR or PR by CRAC, whichever is recorded first) to the date of the first documented tumor progression (assessed by CRAC) or death due to any cause, whichever comes first. If a subject is still responding (i.e., has not progressed nor died after CR or PR), then the subject's data will be censored at date of the last radiographic assessment by CRAC. For subjects who never experienced CR or PR, these subjects' data will not be included in the duration of response analysis.

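### Protocol and SAP define confirmed response (4–6 vs 4–8 weeks) and clinical benefit (no SD minimum vs SD of at least 12 weeks) differently, and neither says which rule prevails

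*Protocol*

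**What the plan says.** **Confirmation of response.** Protocol 5.3.1.1 (Disease/Response Assessment) says "tumor measurements must be confirmed by repeat assessments performed no less than 4 and no more than 6 weeks" after the response criteria are first met, and Protocol 8.1.5 repeats the rule for the analysis: responses must be "confirmed by repeat assessments performed no less than 4 and no more than 6 weeks after the criteria for response are first met". SAP 11.1 has responses "confirmed by repeat measurements performed no less than 4 and no more than 8 weeks after the criteria for response are first met".

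**Clinical benefit.** Protocol 8.1.5: "Clinical benefit includes complete response (CR), partial response (PR), and stable disease (SD) assessed by the CRAC based on RECIST v1.1". No minimum duration of SD is given there or in Appendix H. SAP 11.2 counts confirmed CR or PR, or "stable disease (SD) for at least 12 weeks (2 tumor assessments) as adjudged by the CRAC".

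**Duration of response.** Protocol 8.1.5: "Only subjects with an objective response will be included in the analysis of duration of response (DOR"). SAP 11.2: "Only subjects with a confirmed objective response will be included in the analysis of duration of response (DOR"). Protocol 8.1.5 itself defines objective response as confirmed CR or PR, so under both documents the confirmation window decides who enters the DOR analysis.

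**Schedule.** Protocol Appendix C, footnote s: "Radiographic assessments will occur every 6 weeks", within 1 week either way, to week 30 and every 9 weeks after that. Appendix D, footnote r, gives the same schedule for Arm B.

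**Status.** Protocol 8.0 drops efficacy testing but keeps analysis of the efficacy endpoints by the original methods. SAP 4.0 describes the SAP as a draft, to be finalised before any comparison by arm.

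**The concern.** The same subject can be a responder, enter the DOR set, or have clinical benefit under one document and not under the other. A response confirmed at day 50 counts under the SAP only. A subject with SD at week 6 who progresses before week 12 has clinical benefit under the Protocol only. If no governing rule is written down, the choice falls to whoever programs the endpoint, in an open-label trial. Type I error is not at stake, because Protocol 8.0 rules out efficacy testing. What is at stake is the meaning and reproducibility of the reported ORR, DOR and CBR.

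**Working it through.** The plan gives no figure for either effect, so there is nothing to reproduce. The sizes below are illustrations under stated assumptions.

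**Inputs**
- Confirmation windows: 28–42 days (Protocol 5.3.1.1 and 8.1.5); 28–56 days (SAP 11.1).
- Scans every 42 days to week 30, then every 63 days, each within 7 days of its due date (Protocol Appendices C and D).
- Median PFS: 2.7 months on topotecan (Protocol 3.1); 3.9 months in the third-line Phase 2 data (Protocol 3.3).
- Phase 1 cohort: 8/26 with confirmed response, 22/26 with clinical benefit (Protocol 3.3).
- 1 month = 30.4375 days (SAP 11.1.1).

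**1. Gap between consecutive scans, 6-weekly phase.** Gap = 42 + b − a, where a and b are the two scans' offsets from their due dates. With both within 7 days, the range is 42 − 14 = 28 to 42 + 14 = 56 days. That is exactly the SAP window. The Protocol cap cuts it at 42.

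**2. Share of gaps over 42 days.** Assume a and b are independent and uniform on the integers from −w to w. Then P(gap > 42) = P(b > a) = w/(2w + 1).

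| w (days) | P(gap > 42) |
|---|---|
| 0 | 0 |
| 1 | 1/3 = 0.333 |
| 3 | 3/7 = 0.429 |
| 7 | 7/15 = 0.467 |

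A separate scan at 4–6 weeks satisfies both windows, so only responders who rely on the next routine scan are exposed. At w = 7, reliance of 0%, 25%, 50% and 100% gives 0, 0.25 × 0.467 = 0.117, 0.50 × 0.467 = 0.233, and 0.467. The documents do not give the reliance share.

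**3. 9-weekly phase.** Gap = 63 ± 14 = 49 to 77 days. None falls in 28–42. Of the 15 × 15 = 225 offset pairs, 36 give 49–56 days, so 36/225 = 0.16 fall in the SAP window. A separate scan is needed under either document.

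**4. Effect of the SD minimum.** Use the share progression-free at 6 and 12 weeks as a stand-in for CBR without and with the 12-week rule. With exponential PFS, S(t) = 0.5^(t/m).

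| Median | m (days) | S(42) | S(84) | Difference |
|---|---|---|---|---|
| 2.7 months | 82.2 | 0.702 | 0.492 | 0.209 |
| 3.9 months | 118.7 | 0.783 | 0.612 | 0.170 |

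As a check on shape, take Weibull PFS, S(t) = 0.5^((t/m)^k), at the 2.7-month median. With k = 0.7 the difference is 0.648 − 0.495 = 0.154 (about 15 points). With k = 1.5 it is 0.776 − 0.489 = 0.288 (about 29 points).

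**5. How much of CBR is SD.** In the Phase 1 cohort, 22 − 8 = 14 subjects counted through SD, if all responders are among those with clinical benefit: 14/22 = 64% of those with benefit and 14/26 = 54% of the cohort. That study's SD rule is not given.

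**6. The SAP's own SD wording.** The second scan is due at day 84, in window from 84 − 7 = 77 to 84 + 7 = 91 elapsed days from randomization. SD at a scan on elapsed days 77–83 meets the two-assessment condition but not 12 weeks, if time is counted from randomization.

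**7. Which document governs.** Protocol 8.1 says only that the SAP will add detail. Protocol 8.0 keeps the original methods without naming a document. SAP 4.0 says it follows a draft of Amendment 4. None of these ranks one rule over the other.

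**The case against.** - **Low stakes.** No efficacy testing is planned, SAP 5.1.3 makes ORR and DOR exploratory, and SAP 11.2 makes DOR descriptive with no arm comparison. This is right and limits the severity. CBR, however, is still a secondary endpoint in SAP 5.1.2, and all these endpoints will still be reported.
- **The SAP is an unfinished draft.** It still carries 497 deaths and an interim analysis, against 489 deaths and no interim in the Protocol, so it needs general realignment anyway. True, but realignment will settle these two definitions only if someone decides them.
- **The Protocol's silence on SD duration may simply leave room for the SAP's detail.** That reading is possible. But the Protocol's definition can be programmed as written, and it then gives a different count.
- **The 47% assumes sites skip the 4–6 week scan that the Protocol requires.** Correct: the effect is 0% when sites comply. The imaging footnotes in Appendices C and D list only the 6- and 9-weekly scans, so reliance on the next routine scan is plausible, but its frequency is unknown.
- **The 17–21 point range is too narrow.** It varies only the median. The Weibull cases widen it to about 15–29 points. This stands as a caution about precision and does not remove the discrepancy.
- **Preferring 4–8 weeks counts more responses in an open-label trial already stopped over survival.** The window should be chosen because it fits the scan schedule, and fixed before any comparison by arm.

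**Conclusion.** The discrepancy is real, lies in current text, and is not resolved by either document. Which rule is programmed decides who is a responder, who enters DOR and who has clinical benefit.

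For confirmation, the loss under the Protocol cap is between 0% and about 47% of responses in the 6-weekly phase. The upper end assumes sole reliance on the next routine scan and uniform scatter of 7 days either way. No ORR figure is derived, since the 16% Phase 2 rate in Protocol 3.3 is already a confirmed rate.

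For CBR, the SD rule could shift the within-arm rate by roughly 17–21 points under exponential PFS, and by about 15–29 under the other shapes tried. Nothing is claimed about the difference between arms, and the number of subjects whose status turns on a scan at days 77–83 is unknown.

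The effect is confined to reported estimates. It should be corrected, but it does not threaten the trial's primary conclusion.

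**What to change.** Before the SAP is finalised and before any comparison by arm:

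1. State one confirmation window for the analysis in both documents, such that an in-window next scan in the 6-weekly phase is not rejected. The SAP's existing 4–8 weeks does this. Reconcile Protocol 5.3.1.1 and 8.1.5 with it, by amendment or by recording it in the SAP as a stated change from the Protocol.
2. State one CBR definition, chosen by the sponsor, in both documents, and report the other as supplementary.
3. If the 12-week SD minimum is kept, word it so that the in-window week-12 scan counts. That means 77 or more elapsed days from randomization, which is Study Day 78 or later under the SAP 7.0 convention.

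The cost is SAP wording and programming. Changing the Protocol text needs an amendment with IEC/IRB approval (Protocol 9.1); recording the change in the SAP avoids that. Some responses confirmed after 6 weeks would then be counted. Who assesses response, CRAC or the investigator, also needs settling before programming. It is a separate point that this edit does not resolve.

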#### **8.1.6 Patient Reported Outcomes (PROs)**

The EORTC QLQ-C15-PAL/LC13 scoring manual will be used to transform the raw scores into the domain scores (global health, functional scales, symptom scales/items). Physical functioning domain of the QLQ-C15-PAL PRO questionnaire is a secondary endpoint in the hypothesis testing hierarchy (see Section 8.3). The other scales will be analyzed on an exploratory basis. Change from baseline of the items and domains of the QLQ-C15-PAL/LC13 will be summarized by treatment arm. The EQ-5D-5L manual and the published weights will be used to convert the individual items to the utility scores. Change from baseline of the EQ-5D-5L utility score and VAS will be summarized by treatment arm.

Treatment group differences will be evaluated by analyzing the change from baseline using a one-way analysis of variance (ANOVA) model. Proportion of subjects with clinically meaningful worsening in physical functioning will be compared between the treatment arms.

### **8.1.7 Pharmacokinetic and Exposure-Response Analyses**

Serum concentrations of rovalpituzumab tesirine ADC as well as the incidence and timing of ATA formation will be tabulated and summary statistics will be computed. Serum concentration and ATA data from this study may be combined with data from other studies and analyzed using population pharmacokinetic methodologies.

The relationship between pharmacokinetics (e.g., exposure) and clinical trial findings including, but not limited to demographics, efficacy, and/or safety measures may also be explored. Additional analyses will be performed if useful. Results of the population pharmacokinetic and exposure-response analyses will be provided in a separate report.

